8.1.1.7 Modified Work Productivity and Activity Impairment questionnaire (mWPAI)

Work Productivity and Activity Impairment Questionnaire is commonly used to assess the impact of different health conditions including gynecological indications on absenteeism, presenteeism and activity impairment (28). Modified version for Endometriosis (mWPAI) with 6 items with recall over past 4 weeks will be used. The items will be analyzed descriptively, there is no total score. The data will be collected on eDiary during the site visits as indicated in the SoA (29, 30).

8.1.1.8 Pain Catastrophizing Scale (PCS)

The Pain Catastrophizing Scale (PCS) is a 13-item instrument derived from concepts of catastrophizing described in the literature (Chaves & Brown, 1987; Spanos et al., 1979) as well as items from the catastrophizing subscale of the Coping Strategy Questionnaire (31).

The PCS instructions ask patients to reflect on past painful experiences, and to indicate the degree to which they experienced each of 13 thoughts or feelings when experiencing pain, on 5-point scales with the end points (0) not at all and (4) all the time. The PCS yields a total score and three subscale scores assessing rumination, magnification and helplessness. The total score is computed by summing responses to all 13 items. PCS total scores range from 0 – 52 (32).

The PCS data will be collected on paper at baseline as an explorative endpoint to better understand pain-related distress experienced by women with endometriosis. The results will be reported descriptively without applying any cut-off points or thresholds.

27 JAN 2022 Page: 56 of 99

8.1.1.9 Additional daily symptom items

Three additional items will be asked and reported daily by patient on eDiary to assess dyschezia (pain associated with bowel movement), dysuria (pain associated with urination) and number of hot flushes. These questions will be completed by the study participant each evening (between 18:00 and 24:00) together with the ESD.

The patients will be asked to report pain at its worst during the past 24 hours on 0-10 NRS scale to assess dyschezia and dysuria. These items were derived from previous qualitative research and development of ESD.

In addition, the number of hot flushes (sensation of heat with sweating) in the past 24 hours will be reported to assess tolerability of different active treatments.

8.2 Safety Assessments

Planned time points for all safety assessments are provided in the SoA.

8.2.1 Physical and Gynecological Examinations

- Physical examination includes, at a minimum, assessments of the skin, the lungs, cardiovascular system and abdomen (liver and spleen).
- Gynecological examination is to be done according to local guidelines/common clinical practice.
- Investigators should pay special attention to clinical signs related to previous serious illnesses.
- In the event of any suspicious finding during examinations, further diagnostic investigations should be performed at the discretion of the investigator.
- Abnormal examination findings are to be recorded either as medical history or as AEs (see Section 8.3.1).

Height and weight will be measured and recorded. For weight measurement the participant may wear indoor clothing with no shoes. The clothing should be alike at all measurements.

8.2.2 Vital Signs

Blood pressure and heart rate will be assessed. Measurements should be:

- Preceded by at least 5 minutes of rest for the participant in a quiet setting without distractions
- Assessed in a sitting position
- 1 heart rate and 1 blood pressure reading. The readings will be recorded in the eCRF, as well as corresponding AEs or medical history, if clinically relevant.

8.2.3 Ultrasound

- Ultrasound examination should be performed by a physician well experienced in gynecology or with corresponding qualification based on local clinical practice
- Preferably the evaluation should be performed by transvaginal ultrasound. However, if deemed appropriate, transabdominal or transrectal ultrasound examinations can be performed in addition or instead. The chosen method (s) should be used consistently throughout the study.

27 JAN 2022 Page: 57 of 99

- The following safety parameters will be measured and recorded:
 - Endometrial thickness (measured in the medio-sagittal section as double-layer in millimeters)
 - Evaluation of the ovaries
 - Endometriosis
 - o Adenomyosis
 - o Any other pathology detected during the examination
- In case of any suspicious finding, further diagnostic investigations should be performed at the discretion of the investigator.
- The minimum documentation will include printouts and/or CDs with images from the ultrasound machine showing the endometrium in sagittal section and both ovaries. The printouts and/or CDs with images have to be labeled unambiguously, containing at least the study number, participant number, time point, endometrial thickness, and laterality (left/right) for ovaries. If the printouts are on thermo-sensitive paper, they need to be copied as they will fade over time.

8.2.4 Cervical cytology

- Cervical smear should be obtained at Visit 1a or shortly after Visit 1a.
- Cervical smear performed during the last 12 months prior to Visit 1a can be used for the screening assessment.
- Participants with ASCUS are eligible for the study if they have negative result for high-risk HPV strains from an HPV deoxyribonucleic acid test.
- Cervical smear can be repeated once in case of insufficient material in the sample.
- Cervical smear will only be performed before randomization to ensure eligibility and is not a safety endpoint.

8.2.5 Clinical Safety Laboratory Assessments

- See Section 10.2 for the list of clinical laboratory tests to be performed and to the SoA for the timing and frequency.
- The investigator must review the laboratory report, document this review, and record any clinically significant changes occurring during the study as an AE. The laboratory reports must be filed with the source documents.
- Abnormal laboratory findings associated with the underlying disease are not considered clinically significant unless judged by the investigator to be more severe than expected for the participant's condition.
 - o If clinically significant values do not return to normal/baseline within a period of time judged reasonable by the investigator, the etiology should be identified, and the sponsor notified.
 - All protocol-required laboratory tests, as defined in Section 10.2, must be conducted in accordance with the laboratory manual and the SoA.
 - o If laboratory values from non-protocol specified laboratory tests performed at the institution's local laboratory require a change in participant management or are considered clinically significant by the investigator (e.g., SAE or AE), then the results must be recorded.

27 JAN 2022 Page: 58 of 99

- Laboratory tests may be repeated once prior to Visit 1b in case it is medically justified, and the investigator expects a non-exclusionary result, with the exception of ALT, AST, AP and hepatitis B and C related tests
- For information regarding laboratory assessments related to liver safety, see Section 10.6.

8.2.6 Pregnancy Testing

All participants of the study are women of childbearing potential, thus should receive pregnancy tests according to the SoA. Additionally, the participant is asked to conduct home urine pregnancy testing whenever there is suspicion of a pregnancy (See Section 10.4)

8.2.7 Suicidal Ideation and Behavior Risk Monitoring

Suicidal ideation and behavior have been reported in patients treated with the active comparator (elagolix) (please see section 2.3.1). Therefore, after the start of study intervention, participants should be

- Monitored for new or worsening depression, anxiety or other mood changes, as well as any unusual changes in behavior. Participants with such signs should be referred to a mental health professional, as appropriate.
- Advised to seek immediate medical attention for suicidal ideation or behavior.
- Put through a risk assessment where all possible factors contributing to suicidal ideation and behavior are evaluated and discontinuation of the study intervention is considered

8.3 Adverse Events (AEs), Serious Adverse Events (SAEs) and Other Safety Reporting

The definitions of AEs and SAEs can be found in Section 10.3.

AEs will be reported by the participant (or, when appropriate, by a caregiver, surrogate, or the participant's legally authorized representative).

The investigator and any qualified designees are responsible for detecting, documenting, and recording events that meet the definition of an AE or SAE and remain responsible for following up AEs that are serious, considered related to the study intervention or study procedures, or that caused the participant to discontinue the study intervention (see Section 7).

The method of recording, evaluating, and assessing causality of AEs and SAEs and the procedures for completing and transmitting SAE reports are provided in Section 10.3.

8.3.1 Time Period and Frequency for Collecting AE and SAE Information

All AEs and SAEs will be collected from the signing of the ICF until the follow-up visit, i.e., Visit 6 or 7, respectively, at the time points specified in the SoA (Section 1.3).

Additional details on smell and taste related AEs will be collected once at the end of an individual's study participation via dedicated eCRF pages.

All SAEs will be recorded and reported to the sponsor or designee immediately and under no circumstance should this exceed 24 hours of learning of the event, as indicated in Section 10.3. The investigator will submit any updated SAE data to the sponsor within 24 hours of it being available.

27 JAN 2022 Page: 59 of 99

Investigators are not obligated to actively seek information on AEs or SAEs after conclusion of the study participation. However, if the investigator learns of any SAE, including a death, at any time after a participant has been discharged from the study, and he/she considers the event to be reasonably related to the study intervention or study participation, the investigator must promptly notify the sponsor.

8.3.2 Method of Detecting AEs and SAEs

Care will be taken not to introduce bias when detecting AEs and/or SAEs. Open-ended and non-leading verbal questioning of the participant is the preferred method to inquire about AE occurrences.

8.3.3 Follow-up of AEs and SAEs

After the initial AE/SAE report, the investigator is required to proactively follow each participant at subsequent visits/contacts. All SAEs will be followed until resolution, stabilization, the event is otherwise explained, or the participant is lost to follow-up (as defined in Section 7.3). Further information on follow-up procedures is provided in Section 10.3.

8.3.4 Regulatory Reporting Requirements for SAEs

- Prompt notification by the investigator to the sponsor of an SAE is essential so that legal obligations and ethical responsibilities towards the safety of participants and the safety of a study intervention under clinical investigation are met.
- The sponsor has a legal responsibility to notify both the local regulatory authority and other regulatory agencies about the safety of a study intervention under clinical investigation. The sponsor will comply with country-specific regulatory requirements relating to safety reporting to the regulatory authority, IRBs/ IECs, and investigators.
- For all studies except those utilizing medical devices investigator safety reports must be prepared for SUSAR according to local regulatory requirements and sponsor policy and forwarded to investigators as necessary.
- An investigator who receives an investigator safety report describing an SAE or other specific safety information (e.g., summary or listing of SAEs) from the sponsor will review and then file it along with the IB and will notify the IRB/IEC, if appropriate according to local requirements.

8.3.5 Pregnancy

- Details of all pregnancies will be collected after the start of study intervention and until the end of study. Time period for reporting pregnancies should align with the time period for post-intervention contraception determined in Section 5.1.
- If a pregnancy is reported, the investigator will record pregnancy information on the appropriate form and submit it to the sponsor within 24 hours of learning of the pregnancy.
- While pregnancy itself is not considered to be an AE or SAE, any pregnancy complication or elective termination of a pregnancy for medical reasons will be reported as an AE or SAE.

27 JAN 2022 Page: 60 of 99

- Abnormal pregnancy outcomes (e.g., spontaneous abortion, fetal death, stillbirth, congenital anomalies, ectopic pregnancy) are considered SAEs, and will be reported as such.
- The participant will be followed to determine the outcome of the pregnancy. The investigator will collect follow-up information on the participant and the neonate and the information will be forwarded to the sponsor.
- Any post-study pregnancy-related SAE considered reasonably related to the study intervention by the investigator will be reported to the sponsor as described in Section 8.3.4. While the investigator is not obligated to actively seek this information in former study participants, he or she may learn of an SAE through spontaneous reporting.
- Any participant who becomes pregnant while participating in the study will discontinue study intervention.

8.3.6 Taste Related AEs

- Taste-related AEs will be recorded if reported by the participant
- At the EoT visit, there will be additional questions posed to those participants who spontaneously reported a taste-related AE which occurred during the intervention period:
 - Question for frequency
 - o Question on how bothersome the taste effect was
- Additional details on smell and taste related AEs will be collected once at the end of an individual's study participation via dedicated eCRF pages.

8.3.7 Adverse Events of Special Interest

Adverse events of special interest have to be reported to the sponsor along the timelines set for SAEs, i.e. within 24 hours of the investigator's awareness, as described in Section 8.3.1.

Declaration of an event as serious should only occur if one or more of the serious criteria is applicable. Non-serious adverse events of special interest should not automatically be upgraded to serious by the reporting investigator.

Adverse events of special interest are liver enzyme increases meeting the following criteria:

- ALT and/or AST >8x ULN OR
- ALT and/or AST >3x ULN with total bilirubin >2x ULN.

8.4 Pharmacokinetics

• PK samples will be collected from participants in treatment groups 1-4 to maintain blinding; however, PK samples from the placebo treatment group will not be analyzed (placebo samples might be analyzed e.g. in case of suspected treatment errors).

27 JAN 2022 Page: 61 of 99

- Sparse blood PK samples will be collected for measurement of plasma concentrations of BAY 1817080 as specified in the SoA:
 - Pre-dose sample will be taken at Visits 2, 3 and 5, at least 10 hours after the
 previous dose (NA for Visit 2). Study intervention will be administered at the
 study site after the pre-dose sample at these visits. The following must be
 recorded:
 - Time of the last dose taken at home before the site visit
 - Time of the closest food intake before or after that last dose taken at home
 - Time of the closest food intake before or during dose taken at the site.
 - Two post-dose samples will be taken at Visit 2 and 5: first sample 2 (±1) hours and the second sample 4 (±1) hours after the first daily dose, with at least 1 hour between. Time of the closest food intake before or after the dose must be recorded.
 - One post-dose sample will be taken at Visit 4, at least 5 hours after the previous dose taken at home. The following must be recorded:
 - Time of the previous dose taken at home before the site visit
 - Time of the closest food intake before or after that first dose taken at home
- It is of importance that the actual date and time (24-hour clock time) of blood sampling are documented in the eCRF because PK calculations will be based on the actual sampling times relative to dosing times.
- A maximum of 2 samples may be collected at additional time points during the study if warranted and agreed upon between the investigator and the sponsor. The timing of sampling, may be altered during the course of the study based on newly available data (e.g., to obtain data closer to the time of peak plasma concentrations) to ensure appropriate monitoring.
- Plasma concentrations of BAY 1817080 from sparse PK sampling will be determined using validated analytical methods.
- Samples will be used to evaluate the PK of BAY 1817080 as an exploratory endpoint in this study.

Drug concentration information that may unblind the study will not be reported to investigative sites or blinded personnel until the study has been unblinded.

Detailed instructions about the collection, processing, storage and shipment of biological samples will be provided separately (e.g. sample handling sheets or laboratory manual).

Population pharmacokinetic (popPK) analysis

The systemic exposure of BAY 1817080, drug-related PD biomarker and/or safety and efficacy measurements collected during the trial might be analyzed using nonlinear mixed effects modeling.

Mixed effects models, e.g., popPK models, describe the relationship between dose and time and variables such as drug plasma concentrations. Both structural and random effects are involved in this relationship. A preliminary popPK compartmental model will be further developed using the concentration of the drug as the dependent variable.

27 JAN 2022 Page: 62 of 99

The potential influence of relevant participant covariates (e.g., body weight) and optionally efficacy, PD biomarkers or safety laboratory parameter can be included in the PK/PD modeling using population approaches. A separate evaluation plan, providing details of the model building process and evaluation will be provided prior to the beginning of the popPK/PD analysis. Results obtained by popPK/PD modeling will be presented in a separate report that may also include PK data from other studies with BAY 1817080 or published PK data on elagolix.

The modeling analyses may be started prior to database lock. If this is applicable, appropriate measures will be taken to maintain blinding of the study team, e.g., data will be stored separately, and members of the study team will neither have access to the randomization list nor to individual data.

Plasma concentration data for all participants will be listed in the clinical study report.

Pharmacodynamic parameters are not evaluated in this study.

8.5 Genetics

Genetic as well as non-genetic analyses may be part of the biomarker investigations in this study if approved by local IECs / IRBs and competent authorities, in all countries except for China. Genetic investigations may be of any kind, except for the whole genome sequencing.

A sample for DNA isolation will be collected from participants who have consented to participate in the genetic analysis component of the study. Participation is optional. Participants who do not wish to participate in the genetic research may still participate in the study. Details on sample handling will be provided separately. See Section 8.6 for details.

8.6 Biomarkers

In this study, genetic as well as non-genetic biomarkers will be investigated in participants from all countries except for China.

- **Timing** see SoA for planned time points of sample collection.
- Sample handling and storage details on the collection, processing, shipment and storage of samples will be provided in separate documents (e.g. sample handling sheets or lab manual). Samples may be stored for a maximum of 15 years (or according to local regulations) following the end of the study at a facility selected by the sponsor to enable further analyses.
- **Medical history information** if any additional information about the status of disease was collected in the course of treatment prior to entry of the participant in the study, the results may be collected in order to include this data in biomarker analyses.
- **Reporting** the results of biomarker investigations may be reported separately (e.g. in a biomarker evaluation report).

8.6.1 Biomarkers Monitoring Disease Activity

Serum and plasma will be investigated for e.g. interleukins, high sensitivity C-reactive protein, and neurotrophins:

• Endometriosis is an inflammatory condition with significantly altered local cytokine and neurotrophin milieu in the peritoneal cavity

27 JAN 2022 Page: 63 of 99

- Concentrations of selected immune- and neurotrophin related BMs have been described as being altered not only locally but also systemically in serum/plasma
- Serum concentrations of CA125, CA19-9 and B2M will be investigated within lab parameters to evaluate their diagnostic and monitoring value in endometriosis patients (see Section 10.2).

Analysis of key steroids (estrogen and progesterone) may be conducted in BM samples and utilized for the analysis of disease activity BMs:

- Many inflammatory BMs undergo cyclical modulation during the menstrual cycle, resulting data will need to be investigated in a cycle-controlled manner
- Study visits are scheduled to reflect the intervention period and do not reflect individual cycle lengths and characteristics

8.6.2 Biomarkers Related to Ovarian Activity

Regular menstrual cycles are considered relevant indicators of reproductive health in women and changes may impact the quality of life. In order to demonstrate that BAY 1817080 has no effect on the menstrual cycle and ovarian activity, parameters indicative of ovarian activity will be assessed in this study.

Following parameters will be taken into account to assess ovarian activity:

- Regular menstrual bleeding
- Serum progesterone >3 ng/mL

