2.3.2 Benefit Assessment

Administration of BAY 1817080 may be associated with the following benefits

- may lead to relief of pain symptoms with long-term benefit, which is expected to be associated with increased quality-of-life and social functioning
- may have disease modifying activity by attenuating neurogenic inflammation
- may prolong the intervals between laparoscopic interventions due to the improvement of symptoms, thereby reducing the overall amount of surgical interventions needed
- is expected to have no impact on the menstrual cycle

Hence there is a potential benefit in developing BAY 1817080 for patients with endometriosis. However, to date only preclinical evidence supports this notion (animal data demonstrated that BAY 1817080 blocks neurogenic inflammation and attenuates inflammatory pain). Accordingly, study 20584 is the first to assess clinical efficacy of BAY 1817080 in patients with endometriosis.

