8.6.2.1 Bleeding Pattern

- Menstrual bleeding pattern can be seen as a noninvasive marker for endocrine status in the studied cycle (33).
- The information on menstrual bleeding will be derived from Item 4 in the ESD (see Section 8.1.1.1).
- Cycle length and bleeding duration as well as an average intensity will be calculated.

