8.6.2.2 Diameter of Ovarian Follicles

- Throughout the cycle, the diameter of the largest healthy follicles, with the exception of the dominant follicle, does not exceed on average 6 mm during the follicular phase and 4 mm during the luteal phase. The dominant follicle has a linear daily diameter growth of 2–3 mm per day, and at the moment of ovulation, the diameter of the dominant follicle is 18–27 mm.
- During the ultrasound examination (see Section 8.2.1), ovarian follicles should be monitored. The size of the largest follicle (if mean diameter > 10 mm) as well as presence of a ruptured follicle or corpus luteum should be recorded in the eCRF.
- Follicles larger than 18 mm, ruptured follicles, as well as structures identified as corpus luteum will be indicative of an ovulatory cycle.

27 JAN 2022 Page: 64 of 99

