8.6.2.3 Serum Progesterone

Serum progesterone will be investigated from blood samples at each visit. Progesterone level ≥ 3 ng/mL (9.5 nmol/L) will be considered indicative of a recent ovulation (33, 34).

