6.4 Safety

All variables in this section will be analyzed descriptively based on the SAF.

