6.4.4 Other safety variables

6.4.4.1 Laboratory parameters

Quantitative data (e.g. laboratory parameters) will be described by the following summary statistics: arithmetic mean, standard deviation, quartiles, median, minimum, and maximum. Safety parameters with categorical data will be summarized by reporting number and percent of participants under such categories.

These summary statistics and the difference to baseline (i.e. pre-dose measurements, performed before the first administration of the study medication) will be presented by intervention.

Subjects with abnormal laboratory values (values out of the reference range) will be summarized using shift tables comparing the baseline to post-baseline measurements by timepoint and also for the worst post-baseline measurement. The worst post baseline measurement includes all post baseline values including laboratory values from unscheduled visits.

Frequency tables will be provided for qualitative data. Laboratory data outside the reference range will be listed and flagged with 'L' for low and 'H' for high. Additional tables with all abnormal values will be presented.

The results of the SARS-CoV-2 tests will be displayed descriptively.

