6.4.4.2 Menstrual bleeding pattern

For the analysis of bleeding pattern, the following measures will be derived based on ESD item 4 and analyzed using descriptive statistical methods overall and by treatment group:

1) number of bleeding / spotting days

Number of days where ESD item 4 is spotting, light, normal, or heavy within the respective 28-day reference period.

2) number of bleeding days (excluding spotting-only days)

Number of days where ESD item 4 is light, normal, or heavy within the respective 28-day window.

3) number of spotting-only days

Number of days where ESD item 4 is spotting within the respective 28-day window.

4) number, mean length, and maximal length of bleeding / spotting episodes

According to (2), an episode is defined as consecutive days where ESD item 4 is spotting, light, normal, or heavy, preceded and followed by at least 2 days without bleeding, i.e. ESD item 4 is none. The number, mean length and maximal length for the respective 28-day window will be calculated.

5) number, mean length, and maximal length of spotting-only episodes

According to (2), an episode is defined as consecutive days where ESD item 4 is spotting, preceded, and followed by at least 2 days without bleeding, i.e. ESD item 4 is none. Episodes of length 1 are possible. The number, mean length and maximal length for the respective 28-day window will be calculated.

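### The protocol aims to demonstrate no effect on the menstrual cycle and ovarian activity, but the SAP plans only by-arm descriptive summaries, which cannot support that statement

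*Protocol*

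**What the plan says.** Protocol 8.6.2 explains why parameters of ovarian activity are collected: "In order to demonstrate that BAY 1817080 has no effect on the menstrual cycle and ovarian activity". It names two parameters, regular menstrual bleeding and serum progesterone above 3 ng/mL. The subsections add detail:

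- Bleeding pattern (8.6.2.1): "Cycle length and bleeding duration as well as an average intensity will be calculated".
- Follicles (8.6.2.2): "Follicles larger than 18 mm, ruptured follicles, as well as structures identified as corpus luteum will be indicative of an ovulatory cycle".
- Progesterone at or above 3 ng/mL (8.6.2.3) "will be considered indicative of a recent ovulation".

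Protocol 2.3.2 lists among the possible benefits that the drug "is expected to have no impact on the menstrual cycle".

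On analysis, Protocol 9.4.5 makes all safety analyses descriptive. SAP 6.4 repeats this: "All variables in this section will be analyzed descriptively based on the SAF". SAP 6.4.4.2 derives five bleeding and spotting measures per 28-day window, to be "analyzed using descriptive statistical methods overall and by treatment group". SAP 6.4.4.1 summarises laboratory parameters by arm ("These summary statistics and the difference to baseline") and adds shift tables. The SAP does not name progesterone, which as a Table 10-1 hormone would fall under these generic summaries. Cycle length, average bleeding intensity, the progesterone classification and the follicle findings do not appear in the SAP.

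**The concern.** Demonstrating no effect is an equivalence-type claim. It needs an estimate of the difference from placebo, an interval around it and, for a firm conclusion, a limit against which to hold the interval. The SAP supplies none of these for bleeding or hormones. A reader would have to compare columns of means and quartiles, and could take the lack of a visible difference as evidence of no effect.

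The claim has some weight because Protocol 2.3.1 lists changed menstrual bleeding as a warning for the comparator elagolix, so a statement of no effect would set BAY 1817080 apart from it. The early stop adds to the problem. Smaller arms make it easier to see nothing, whatever the truth.

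**Working it through.** **The plan's own figure.** The only powered figure concerns pain: about 90% average MCP-Mod power with 50 evaluable per dose group, SD 2.5, maximum effect −1.2 and one-sided alpha 0.10 (Protocol 9.2). Simulating the maximum-contrast test for the four candidate curves gives 0.890, 0.893, 0.931 and 0.909, average 0.906, so it reproduces. It says nothing about bleeding or ovulation, for which the documents give no figure.

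**Which numbers apply.** Bleeding and laboratory data are analysed on the SAF (SAP 6.4), that is, participants who took at least one tablet. The planned size is about 420/5 = 84 per arm. The components of Protocol 9.2 agree for the blinded arms: 70 + (28 + 28)/4 = 84. This is a ceiling, since those never dosed drop out of the SAF. The 50 per arm is the pPPS number for the pain endpoint and is not the right size here.

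**What an interval would show.** In SD units and without covariate adjustment, the half-width of the 95% CI is t(0.975, n1 + n2 − 2) × √(1/n1 + 1/n2).

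| Comparison | Half-width |
|---|---|
| One dose v placebo, 84 v 84 | 1.974 × 0.1543 = 0.30 SD |
| Pooled BAY v placebo, 252 v 84 | 1.967 × 0.1260 = 0.25 SD |
| One dose v placebo, 30 v 30 (assumed) | 2.002 × 0.2582 = 0.52 SD |
| One dose v placebo, 20 v 20 (assumed) | 2.024 × 0.3162 = 0.64 SD |

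The last two sizes are assumptions, because the documents give no final N. Adjusting for the baseline window would narrow these intervals by an amount the documents do not allow one to compute.

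On natural scales at 84 per arm (1.96 × SE):

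- Bleeding days per 28 days, assumed SD 2, 3 or 4: ±0.60, ±0.91 or ±1.21 days.
- Proportion with an ovulation marker, assumed 50%, 80% or 90%: ±15.1, ±12.1 or ±9.1 percentage points.

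**How much a lack of difference would exclude.** No test is planned, so a two-sided 5% test serves only as a yardstick. For a true 0.5 SD shift it would miss:

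- 10% of the time at 84 v 84
- 2% at 252 v 84 (pooled BAY)
- 52% at 30 v 30
- 66% at 20 v 20

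For a fall in ovulation rate from 80% to 65% (assumed rates), power at 84 per arm is 59%, so 41% would be missed.

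**Would a margin rule work?** With no true effect, the chance that the 95% CI for one dose v placebo lies wholly within ±0.5 SD is 79% at 84 per arm, 4% at 30 and about 0% at 20. A compulsory margin would therefore almost never be met after a severe shortfall.

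**The case against.** Four points on the other side have force.

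1. **It is not a trial objective.** Section 3 has no menstrual or ovarian objective, Section 9.1 has no such hypothesis, and type I error is controlled for the primary analysis only. The sentence in 8.6.2 gives a reason for collecting data, and 2.3.2 speaks of an expectation. No rule in either document concludes no effect. This stands and limits the point to a minor one.
2. **Other plans may cover it.** Protocol 9.4.6 sends selected biomarker analyses to separate plans, and 9.5 names a Biomarker SAP. These were not supplied and might compare hormones with placebo. This stands for hormones. Bleeding pattern, however, is analysed in the SAP at hand, and only descriptively.
3. **The planned size is not poor.** A reader might infer that a half-SD change would often go unnoticed at the planned numbers. The documents do not support that. It comes from applying the 50 evaluable for pain to data analysed on the SAF. At about 84 per arm the miss rate is 10%, and for pooled BAY 1817080 it is 2%. The stronger reading holds only at the assumed post-stop sizes, or for a binary marker such as ovulation.
4. **The study has ended for liver safety**, so little may hang on this result. That lowers the stakes, but the report can still make or avoid the statement.

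Two replies do not succeed. The general 95% CI convention in SAP 4.1 fixes a confidence level but names no contrast. Nor does a descriptive safety section rule out a comparison: SAP 6.4.1.1 already plans a logistic model with odds ratios and CIs for taste-related events.

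**Conclusion.** The point holds as a minor mismatch between a stated aim and the planned analysis. Protocol 8.6.2 speaks of demonstrating no effect. The supplied SAP gives by-arm summaries on the SAF without a difference from placebo or an interval, so it cannot support such a statement. The primary and secondary analyses are untouched.

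At the planned size an interval would be informative for a continuous measure: about ±0.30 SD for one dose and ±0.25 SD for pooled BAY 1817080. At an assumed 20 per arm it widens to ±0.64 SD. The SDs in days, the ovulation rates and the post-stop arm sizes are assumptions. The conclusion about hormones depends on what the separate biomarker plans contain. It does not follow that the study was too small as planned, or that a no-effect conclusion is bound to be reported.

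**What to change.** - **SAP 6.4.4.2:** for each BAY 1817080 dose and for pooled BAY 1817080 v placebo, on the SAF, add the baseline-adjusted difference in bleeding/spotting days per 28-day on-treatment window with a two-sided 95% CI.
- **Also in the SAP:** add the difference in proportions v placebo, with 95% CI, for the two parameters named in 8.6.2: regular menstrual bleeding, and progesterone above the protocol cut-off. Bleeding days alone would not address regularity or ovulation. This needs a definition of regular bleeding, and one form of the cut-off, which is written as above 3 ng/mL in 8.6.2 and as 3 ng/mL or more in 8.6.2.3. If a separate biomarker plan already contains the hormone comparison, a cross-reference is enough.
- **Protocol 8.6.2:** replace the aim of demonstrating no effect with that of estimating the effect of BAY 1817080 as the difference from placebo with a 95% CI.
- **Margin:** optional, and for the sponsor to justify before unblinding. Without one, the report should give the intervals and draw no conclusion of no effect.

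The cost is some wording and a few simple models on data already collected. The downside is that, after the early stop, the intervals will probably be too wide to support a claim of no effect. Reporting them would make that visible.
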